## 1. STUDY SUMMARY AND AIMS

### Rationale:

In 2013, WHO recommended that all HIV-infected pregnant women receive lifelong antiretroviral therapy for prevention of mother-to-child transmission (PMTCT-ART). This approach provides treatment and prevention benefits but there are concerns about its risks if maternal retention in care or adherence falters. Mobile health (mHealth) SMS (short message system) messaging is an evidence-based intervention that has been shown to significantly decrease treatment failure in adult ART treatment programs in Africa and may provide an inexpensive, feasible approach to enhance PMTCT-ART outcomes while supplementing rather than adding to provider workload. Our overarching hypothesis is that investment in mHealth for retention and adherence in PMTCT-ART will provide cost-effective benefit in sustaining antiretroviral regimen efficacy and durability.

**Design:** A 3-arm, unblinded, randomized clinical trial (RCT) comparing the effects of unidirectional SMS (ie: “push” messaging to participant) vs. bidirectional SMS dialogue between participant and provider vs. control (no SMS) among HIV-infected Kenyan mothers in PMTCT-ART programs.

**Population:** Pregnant HIV-positive women  $\geq 14$  years old and  $\leq 36$  weeks pregnant.

**Sites:** Ahero Sub-district Hospital (Kisumu, Kenya), Bondo District Hospital (Kisumu, Kenya), Mathare North City Council Clinic (Nairobi, Kenya)

**Sample Size:** 825 women will be randomized (275 per study arm)

**Duration:** Follow-up through 2 years postpartum

### Specific Aims:

**AIM 1:** To compare mother-infant pairs receiving systematic, tailored unidirectional SMS messaging vs. bidirectional SMS dialogue vs. control (no SMS) for outcomes measured during 2-year postpartum follow-up, including:

- a) Maternal retention in care, ART refills, virologic non-suppression, and ART drug resistance
- b) Infant HIV infection and HIV-free survival
- c) Maternal perceptions of acceptability, utility and strengths/weaknesses of unidirectional and bidirectional SMS

*Hypothesis 1: Long-term retention, ART adherence, and maternal/infant outcomes will be enhanced by SMS. Mothers will endorse SMS approaches, preferring bidirectional messaging dialogue.*

**AIM 2:** To determine correlates of maternal treatment failure (loss to follow-up, virologic non-suppression, or ART resistance) and correlates of infant HIV infection in the cohort overall and stratified by arm, and characterize SMS interactions among women in the bidirectional SMS arm, including frequency of and changes in interactivity over time, relationship to pivotal time-points (delivery, cessation of breastfeeding, transfer of care to ART clinic), characteristics of high and low ‘interactors’, and topics motivating interactions.

*Hypothesis 2: Lack of disclosure to partner, distance to clinic, and poor understanding of need for lifelong ART, will be associated with maternal treatment failure. Interaction frequency with bidirectional SMS will decline over time, and ‘higher-interactors’ will be younger, primigravida, and more educated.*

**AIM 3:** To assess the cost-effectiveness of unidirectional SMS and bidirectional SMS interactions: a) Estimate net cost savings realized through the reduction of treatment failure and drug resistance. b) Estimate incremental cost-effectiveness in improving infant and maternal health outcomes.

*Hypothesis 3: Both interventions will be cost saving and cost-effective; bidirectional SMS will be more cost-effective.*

**Note: this Statistical Analysis Plan focuses on AIM 1.**

Clinical Trials registration: <https://clinicaltrials.gov/ct2/show/NCT02400671>

## 2. STUDY ENDPOINTS

Primary study endpoints:

1. **Virologic non-suppression** will be defined for the primary endpoint using plasma viral load cut-off HIV RNA  $\geq 1000$  copies/mL for primary endpoint based on sample detection limits. A secondary cutoff at assay limit of detection (20c/ml for plasma and 839c/ml for DBS) will also be assessed.
2. **Retention in care** will be assessed based on medical record review of clinic attendance for scheduled clinical visits. Retention will be defined per participant as the proportion of scheduled visits to date attended within 2 weeks of their scheduled time and will be evaluated at 12 and 24 months postpartum. Loss to follow-up will be defined as no clinical visits for at least 6 months and will be evaluated at 12 and 24 months postpartum. Initial analyses will examine the 0-365 day interval and the 0-730 day interval.
3. **Infant HIV-free survival** will be assessed using infant HIV test and infant mortality data.

Secondary endpoints:

1. **ART adherence** will be assessed based on pharmacy refill data. For each refill period throughout the study, the proportion of days covered will be based on timing of refill collection. Self-reported adherence will also be assessed at study visits using a standardized questionnaire of the number of pills missed in the last 30 days and calculating percent adherence based on the expected number of doses taken. Self-reported adherence will be compared in secondary analyses.
2. **Drug resistance** will be assessed as detection of drug resistance mutations from plasma of women with HIV RNA  $\geq 1000$  copies/mL using the Oligonucleotide Ligation Assay (OLA).

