Computer Science and Engineering collaborators. Between study visits, data will be obtained from patient records in order to inform personalized, dynamic messaging. For example, if a participant in one of the intervention arms misses an appointment an appropriate SMS will be sent to address this absence and encourage the participant to reschedule. If a participant in the bidirectional arm does not respond after receiving two weekly messages, she will receive a check-in message asking if she is receiving messages. The study nurse will review clinical records daily to check for missed appointments, deliveries, clinic visits, infant immunizations, or any clinic contact from study participants. Delivery information from women will be obtained at 6 weeks postpartum and data abstracted from records at MCH-linked maternity centers. Follow-up will continue until 24 months postpartum.

In order to ensure completeness of clinic record abstraction for the study period, photographs will be taken at study exit of participants' CCC cards. All identifiable information, including name, date of birth, CCC number, ANC number and address will be covered with paper, and the record will be labeled with the participant's study ID only. Photographs will be transferred to a password-protected computer and secure server within 1 day of the photograph being taken and permanently deleted from the device used to capture the image. At the final study visit, in order to verify the data collected during abstraction, we will measure the height, weight, and mid-upper arm circumference of participants and their infants.

We will collect 14 ml maternal plasma samples for CD4 count, HIV viral load, and suspected drug resistance testing for mothers and 0.5 ml for HIV DNA DBS and HIV antibody testing for infants at all study visits. SOPs will be used to guide venipuncture procedure. The study will obtain viral loads for all participants. However, if the Kenyan MOH incorporates routine HIV viral load testing on a national scale and the testing intervals are similar to those proposed by the study, we will utilize viral load results from the standard of care rather than repeat viral loads.

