**Table 2.1 Summary of primary and secondary endpoints**

Primary Endpoints	Indicator	Source
Maternal virologic non-suppression	HIV RNA $\geq 1000$ copies/mL	Maternal study visits at 6 wk, 6, 12, 18, 24 mo, and record abstraction for routine VL.
Retention	Seen within 2 weeks of scheduled visits	Record abstraction for scheduled clinic visits throughout study.
Loss to follow-up	Not seen in clinic for $\geq 6$ months	
Infant HIV-free survival	HIV DNA and antibody results, and mortality	Record abstraction, infant study visits, verbal autopsy.
Secondary Endpoints	Indicator	Source
Drug Adherence	Pharmacy: % days covered since last refill Self-report: % doses taken in last 30 days *pharmacy data viewed as primary analysis of secondary endpoint	Pharmacy: record abstraction throughout study Self-report: questionnaire at study visits
Maternal drug resistance	OLA	Resistance assay in mothers with virologic failure

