#### Primary

1. **Viral non-suppression (virus detected at  $\geq 1000$  copies/mL):** Generalized estimating equations (GEE) with log-binomial link will be used to compare the 2-way or 1-way arms versus control arm for prevalence of viral non-suppression at any time during follow-up. All available data will be used after enrollment and  $\geq 4$  months since ART start, but any observed unsuppressed VL within 30 days after an unsuppressed VL will be excluded. As secondary analyses, Andersen-Gill analysis will be used to compare incidence of viral non-suppression in the 2-way or 1-way arms versus control arm at any time during follow-up. The proportions of women ever experiencing viral non-suppression as well as the cumulative incidence by delivery, 180 days postpartum, 365 days postpartum, and 730 days postpartum will be compared between arms by log-binomial regression.
2. **Retention in care.** GEE with log-binomial link will be used to compare arms for proportion of visits attended within 2 weeks of scheduling throughout study follow-up. The proportions of women lost to follow-up by 12 and 24 months postpartum will be compared between study arms by log-binomial regression.
3. **Infant HIV-free survival.** Incidence of infant HIV acquisition or death will be compared between study arms using Cox proportional hazards regression.

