**Adherence**

\$Self-reported adherence <95% over entire

follow-up (%)

\$Refill-based adherence <95% over entire

follow-up(%)

\$ Compared by GEE Log-binomial regression

& Compared by Andersen-Gill regression

^ Compared by Cox proportional hazards regression

\* Compared by Log-binomial regression

+ Exploratory comparison

\*\* All available VL after enrollment and  $\geq 4$  months after ART start will be included

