**Table 6.1. Summary of modifications**

Description of modification	Date of modification	Modified SAP version	Original approach	Updated approach	Justification
Addition of secondary analysis with imputation of missing data (see section 5.5)	27 May 2018	3.0	None specified	A secondary analysis will be performed using multiple imputation by MCMC to impute VL 6 months after the time of last measurement.	Upon further thought, the study team realized that VL data were likely to be missing not at random and an imputed analysis could provide a less biased effect estimate.
Analytical approach for virologic failure primary outcome (see section 5.3)	1 May 2019	4.0	Incidence of virologic failure (HIV RNA $\geq 1000$ copies/mL) after the first 4 months post-enrollment will be compared between study arms using Cox proportional hazards regression.	We will stratify the study population by VL at enrollment, and conduct 2 separate survival analyses: 1. Incidence of virologic suppression among participants with unsuppressed VL at enrollment. 2. Incidence of virologic failure among participants with suppressed VL at enrollment.	Our study population is composed of two distinct groups: those entering the study on established suppressive therapy, and those not on suppressive therapy. The study team realized that the intervention may have distinct mechanisms of action for each group. We will therefore analyze them separately.
Addition of pre-specified secondary analysis of virologic failure (see section 5.7)	1 May 2019	4.0	None specified	Among participants who are virally suppressed at 6 months postpartum, incidence of virologic failure (HIV RNA $\geq 1000$ copies/mL) will be compared between study arms using Cox proportional hazards regression	This analysis will evaluate effects of SMS on longer term viral failure after the early postpartum period.

Addition of VL cutoff for virologic failure outcome (see section 5.3)	26 May 2020	5.0	Virologic failure = HIV RNA $\geq$ 1000 copies/mL	Virologic non-suppression = HIV RNA $\geq$ 1000 (primary) and $\geq$ assay limit of detection (secondary)	Since the study was originally funded, it is understood that levels below 1000 c/ml may be associated with transmission, so there is interest in additional analysis of lower cutoffs.

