Modification of VL analysis approach	26 May 2020	5.0	We will stratify the study population by VL at enrollment, and conduct 2 separate survival analyses: 1. Incidence of virologic suppression among participants with unsuppressed VL at enrollment. 2. Incidence of virologic failure among participants with suppressed VL at enrollment.	Risk of virologic non-suppression will be analyzed as a repeated measure by GEE with Poisson link.  Previously specified analyses of incidence of virologic suppression and virologic failure will be performed as exploratory analyses.	The stratified analysis did not use all available data, or allow us to probe changes in the intervention's effect over time. In order to maximize power and allow estimation of effect modification by peripartum timepoint, we will treat virologic non-suppression as a repeated measure.
Removal of secondary analysis with imputation of missing VL data	26 May 2020	5.0	A secondary analysis will be performed using multiple imputation by MCMC to impute VL 6 months after the time of last measurement.	No imputation will be performed.	Our dataset has 10% missing data at 24 months postpartum but >40% missing data at 18 months postpartum. Imputation of the one final VL measure would not address the problem of missing VL for a repeated measures analysis, since the bulk of missingness is at intervening timepoints. Imputation of intermediate VL given such high levels of missingness is not advisable.

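### Does the detection-limit cutoff, 20 c/mL on plasma but 839 c/mL on DBS, need a written rule for combining the two specimen types?

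*SAP*

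**What the plan says.** SAP section 2 defines primary non-suppression as HIV RNA of at least 1000 copies/mL, a level chosen with the sample detection limits in mind. It then adds: "A secondary cutoff at assay limit of detection (20c/ml for plasma and 839c/ml for DBS) will also be assessed". Table 6.1 (26 May 2020, version 5.0) gives the reason: "levels below 1000 c/ml may be associated with transmission, so there is interest in additional analysis of lower cutoffs".

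On data sources, Table 2.1 lists "Maternal study visits at 6 wk, 6, 12, 18, 24 mo, and record abstraction for routine VL". The protocol (Phase 2, data collection procedures) plans maternal plasma for viral load. It also says that if national routine testing runs at similar intervals, "we will utilize viral load results from the standard of care rather than repeat viral loads". It does not state the specimen type of those routine results.

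On analysis, the viral item in SAP section 5.3 is written for the 1000 c/mL threshold and says "All available data will be used after enrollment", subject to at least 4 months since ART start. A footnote to Table 5.2 repeats this: "All available VL after enrollment". Section 5.3 names no model for the lower cutoff and Table 5.2 has no row for it. Adjustment is for baseline imbalance only.

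**The concern.** The two limits differ about 42-fold (839/20). The same true viral load can be an event on one specimen and a non-event on the other. If the inclusion rule for the primary threshold is carried over to the lower one, both specimen types enter one analysis, and prevalence then depends partly on how many results happened to be on DBS.

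This seems to defeat the purpose of the cutoff. It was added to look below 1000 c/mL, and there a DBS result can register only 839 to 999 c/mL. A DBS result below 839 c/mL would be counted as suppressed although it says nothing about 20 to 838 c/mL. At stake are the reading of the prevalence at this cutoff and, if mix or effect varies, the risk ratio.

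**Working it through.** The documents give no prevalence, power or DBS share for this cutoff, so there is no stated figure to reproduce. The check asks what pooling would do.

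**Inputs from the documents:** limits of 20 c/mL (plasma) and 839 c/mL (DBS); primary threshold 1000 c/mL.

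**Assumptions, not in the documents:** h = share of results at or above 839 c/mL; m = share in 20 to 838 c/mL; d = DBS share. Specimen type is taken as unrelated to true viral load, and assay error is ignored.

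**1. Primary endpoint.** 1000 > 839 > 20, so either specimen can classify a result at 1000 c/mL. The difference in limits does not touch it.

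**2. How much of the sub-1000 range DBS can see.**
- Log scale: log10(1000/839) / log10(1000/20) = 0.0762 / 1.6990 = 4.5%.
- Linear scale: (1000 − 839) / (1000 − 20) = 161/980 = 16.4%.

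These are widths of a range, not shares of results, so they do not measure impact.

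**3. Pooled prevalence** = h + (1 − d)m. It falls from h + m with no DBS to h with all DBS. For h = 15% and m = 10%, that is 25% down to 15%.

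**4. Risk ratio with the same mix in both arms.** Let rH be the ratio at or above 839 c/mL and rL the ratio in 20 to 838 c/mL. The pooled ratio is [rH·h + rL·m(1 − d)] / [h + m(1 − d)]. With h = m = 10%:

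| DBS share | Control prevalence | rH 1, rL 0.70 | rH 0.85, rL 0.70 | rH 0.70, rL 0.70 | rH 0.70, rL 1 |
|---|---|---|---|---|---|
| 0% | 20.0% | 0.850 | 0.775 | 0.700 | 0.850 |
| 5% | 19.5% | 0.854 | 0.777 | 0.700 | 0.846 |
| 10% | 19.0% | 0.858 | 0.779 | 0.700 | 0.842 |
| 30% | 17.0% | 0.876 | 0.788 | 0.700 | 0.824 |
| 50% | 15.0% | 0.900 | 0.800 | 0.700 | 0.800 |

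Example, third column at 10%: (0.10 + 0.70 × 0.10 × 0.90) / (0.10 + 0.10 × 0.90) = 0.163/0.190 = 0.858. Last column at 50%: (0.07 + 0.05) / 0.15 = 0.800.

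The ratio can move toward 1, away from 1 or not at all, depending on whether the effect is stronger, weaker or equal at low levels. If rH = rL = 1 it is 1 at every DBS share, so an equal mix creates no false effect.

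**5. Risk ratio with no true effect but unequal mix.** With h = 15% and DBS shares of 30% against 40%, m = 10% gives (0.15 + 0.60 × 0.10) / (0.15 + 0.70 × 0.10) = 0.21/0.22 = 0.955. For m = 5% and 20% it is 0.973 and 0.931. A false effect needs a mix that differs by arm, and the documents show no such difference.

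**The case for a change.** The strongest case for a change runs as follows. The SAP names a DBS limit inside the maternal endpoint, in a version whose change log already describes the missingness in the data, so some maternal DBS results were at least expected. For the primary endpoint the sponsor chose a threshold above both limits; the secondary cutoff gives up that protection. Version 5.0 also moved to repeated measures in order to study effects by peripartum timepoint, so a mix that drifts over time could disturb that picture. Arm differences are possible too: messaging could change attendance, and attendance could change whether a result comes from a study plasma sample or a routine record. The remedy looks cheap: report by specimen type and tabulate specimen by arm and visit.

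Part of this stands. A pooled prevalence at this cutoff cannot be read without the specimen mix, and a DBS result below 839 c/mL is not evidence of no low-level viraemia. A careful report would say both.

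The rest is weaker. Pooling is inferred: the all-available-data text and the footnote belong to the 1000 c/mL item and to table rows that do not include the lower cutoff. The documents mention maternal DBS only through its detection limit and plan plasma for study samples, so DBS may be rare. Nor is there one clearly better rule. Stratifying, restricting to plasma, adjusting for specimen, or using a common threshold at or above 839 c/mL are all defensible, and each has a cost. A common threshold loses most of the range of interest. A plasma-only reading depends on who had plasma drawn, which is itself open to selection in data with "10% missing data at 24 months postpartum but >40% missing data at 18 months postpartum"; a table would reveal that but not correct it.

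**Conclusion.** No change to the plan is needed. The SAP says how each single result is classified at the detection limit; it leaves unwritten how the two specimen types are presented together. Followed as it stands, it still compares arms on detectability by the assay used, and that comparison is free of false effect as long as specimen mix does not differ by arm. Applying two limits requires specimen type to be known for each result, so analysts can report by specimen, or show the mix, without collecting anything new.

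The size is unknown because the DBS share and viral-load distribution are not given. Under the assumed 10%/10% split and equal mix, a DBS share of 5% to 10% moves the ratio by 0.008 or less; shifts of 0.05 need half of all results on DBS and an effect confined to one part of the viral-load range. The conclusion rests on specimen mix being similar across arms, and it concerns a secondary cutoff only. The 1000 c/mL primary endpoint is unaffected.

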Maternal perceptions of intervention	Standardized questions	At study visits, subset FGD
Cost-effectiveness, cost-savings	Cost/time questions	Interview, clinic
Selected Secondary Outcomes		
Postpartum contraception	Use of effective contraception	MCH card, CRF
Exclusive breastfeeding	Ever, duration	CRF
Infant mortality	Death during follow-up	CRF, verbal autopsy

Notes: MCH: Maternal-Child Health; CRF: case report form

Outcomes

A summary of proposed outcomes is provided above in Table 8 (above). Retention is a primary outcome in this RCT, thus we seek to observe the effect of the intervention on retention rather than using comprehensive strategies to optimize it. To ascertain other outcomes, a relatively low intensity of study visits (6-monthly) has been designed; however, we are aware that this will compromise retention compared to our prior studies with >90% retention in which more frequent study visits facilitated retention. For all arms, we will not trace participants who do not attend clinic with home visits until study end, when we will conduct home visits for final ascertainment of outcomes.

ART adherence is difficult to accurately assess – patient self-report, pill counts, and MEMS-caps (Medication Event Monitoring System caps are able to record the number of bottle openings and the date and time of each opening) have been used with varying success due to subjectivity and need for participant cooperation (43). Drug levels, treatment or virologic failure, and resistance are more objective measures of adherence long-term. We will use simple, standard measures of adherence (pharmacy refills, and self-reported missed doses at study visits) but rely on the viral suppression measurements as the superior outcome marker of adherence.

h) LABORATORY METHODS

We will conduct maternal HIV viral load testing and infant HIV DNA DBS testing at the branches of the KEMRI/Centers for Disease Control (CDC) located in Kisumu and Nairobi, and CD4 testing at the KEMRI/Centers for Disease Control (CDC) located in Kisumu and Kenyatta National Hospital. Test results will be shared with the clinics and providers to help guide clinical care. Among women with detectable virus, drug resistance will be measured using oligonucleotide ligation assays (OLA) in collaboration with [name]. OLA assays will be conducted in [name] laboratory in Seattle Children's Hospital.

i) DATA COLLECTION INSTRUMENTS

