### 3. SAMPLE SIZE CONSIDERATIONS

#### a. Analyses based on comparison of proportions

Assuming alpha=5%, power=80%, 2-sided test, 1:1:1 allocation ratio, with a sample size of 275 per arm, we would have sufficient power to detect an increase in retention or increase in virologic suppression (inverse of virologic failure) from 75% (control) to  $\geq 85\%$ , allowing for 10% attrition; we will also be able to detect an increase in ARV adherence from 85% to  $\geq 95\%$  (Table 6). Thus, the total cohort sample is 825 women. We could see a difference from 75% to 85% between control and unidirectional SMS and additionally detect a difference between uni- and bidirectional SMS (85% to 95%). Similarly, we will have sufficient power to detect an increase in infant HIV-free survival from 85% to  $\geq 95\%$ .

*Sample size for unidirectional or bidirectional SMS vs. control or unidirectional vs. bidirectional; gray shading shows cells with sufficient power and n is number per arm*

Intervention	Prevalence of outcome	Control			
		70%	75%	80%	85%
	85%	120	250	906	-
	90%	62	100	199	686
	95%	35	49	75	140

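### The loss-to-follow-up rule needs a 6-month absence inside windows closing at 12 and 24 months, so those rows count only departures up to about months 6 and 18

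*SAP*

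**What the plan says.** SAP section 2, under retention in care, defines a binary measure: "Loss to follow-up will be defined as no clinical visits for at least 6 months and will be evaluated at 12 and 24 months postpartum". The next sentence sets the windows: "Initial analyses will examine the 0-365 day interval and the 0-730 day interval". Table 2.1 repeats the 6-month rule and lists loss to follow-up among the primary endpoints. SAP 5.3 gives the analysis: "The proportions of women lost to follow-up by 12 and 24 months postpartum will be compared between study arms by log-binomial regression". The Table 5.2 shell has one row for each time point.

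The same SAP section also defines a separate visit-based measure: "Retention will be defined per participant as the proportion of scheduled visits to date attended within 2 weeks of their scheduled time". SAP 5.3 analyses it by GEE over the whole of follow-up.

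The protocol (Phase 2, data collection procedures) says: "Follow-up will continue until 24 months postpartum". Under its outcomes heading it adds: "For all arms, we will not trace participants who do not attend clinic with home visits until study end". Until study end, therefore, attendance records carry the information on loss.

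Neither document dates a loss back to the last visit, says that records after day 365 or day 730 may confirm an absence, or gives a different rule near the end of a window.

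**The concern.** A rule that requires 6 months without a visit can only be met 6 months after a woman leaves. Applied inside a window that closes at 12 months, it cannot see departures in the second half of that window. Applied inside one that closes at 24 months, it cannot see departures in the last quarter. The row labels promise cumulative loss by 12 and by 24 months, but what is counted is departure up to about months 6 and 18.

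For a programme reader, loss is understated in every arm. For the trial, a primary measure has fewer events than its label suggests, and hence less power. At 12 months this is avoidable, because attendance continues to be abstracted for another year.

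**Working it through.** **1. Cut-off days.** Taking day 0 as delivery and 6 months as 182 days: 365 − 182 = day 183, and 730 − 182 = day 548. The blind period is 6 of 12 months (50%) in the first window and 6 of 24 (25%) in the second. This step needs no assumed rate.

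**2. The plan's own sample-size figures.** SAP 3a: "Assuming alpha=5%, power=80%, 2-sided test, 1:1:1 allocation ratio, with a sample size of 275 per arm", "allowing for 10% attrition", for 75% v 85%. With pooled variance and no continuity correction:

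n = [1.960·√(2·0.80·0.20) + 0.842·√(0.75·0.25 + 0.85·0.15)]² / 0.10² = (1.109 + 0.472)² / 0.01 = 250 per arm, which matches the SAP table. After 10% attrition, 275 × 0.9 = 247.5 per arm, with power 79.5% at 247.

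SAP 3b assumes 25 per 100 person-years of loss to follow-up in control and a hazard ratio of 0.65, and tabulates 238 per arm. The Schoenfeld formula gives 4(1.960 + 0.842)²/(ln 0.65)² = 169.2, so 170 events. The tabulated 238 follows if mean follow-up is about 1.73 years, a value the SAP does not state.

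**3. Share of leavers the rule can count.** Assumptions: constant departure hazards of 0.25 (control) and 0.25 × 0.65 = 0.1625 (SMS) per year, no return, and risk starting a years before delivery (a = 0 to 0.5, since women enrol in pregnancy). For a window of W years:

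- left by the end of the window: 1 − exp[−λ(W + a)]
- able to meet the rule: 1 − exp[−λ(W + a − 0.5)]

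Power is for a two-sided 5% comparison of two proportions, at 247 and at 275 per arm.

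| Window | a (months) | Left, control v SMS | Countable, control v SMS | Control leavers uncounted | Power if all leavers counted (n = 247; 275) | Power under the rule (n = 247; 275) |
|---|---|---|---|---|---|---|
| 12 mo | 0 | 22.1% v 15.0% | 11.8% v 7.8% | 46.9% | 53.0%; 57.5% | 31.4%; 34.4% |
| 12 mo | 3 | 26.8% v 18.4% | 17.1% v 11.5% | 36.3% | 61.3%; 66.0% | 43.1%; 47.0% |
| 12 mo | 6 | 31.3% v 21.6% | 22.1% v 15.0% | 29.3% | 68.1%; 72.8% | 53.0%; 57.5% |
| 24 mo | 0 | 39.3% v 27.7% | 31.3% v 21.6% | 20.5% | 78.1%; 82.3% | 68.1%; 72.8% |
| 24 mo | 3 | 43.0% v 30.6% | 35.4% v 24.8% | 17.6% | 81.7%; 85.6% | 73.7%; 78.1% |
| 24 mo | 6 | 46.5% v 33.4% | 39.3% v 27.7% | 15.3% | 84.6%; 88.2% | 78.1%; 82.3% |

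**4. Effect on the comparison.** With a = 0, the uncounted share is 46.9% in control and 48.0% with SMS at 12 months, and 20.5% and 22.0% at 24 months. The risk ratio is 0.678 for all leavers against 0.664 for countable leavers at 12 months, and 0.705 against 0.692 at 24 months.

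**5. Same check with the SAP 3a effect.** Suppose 25% v 15% have truly left by the end of the window, at a constant hazard. Countable loss is then 1 − 0.75^0.5 = 13.4% v 1 − 0.85^0.5 = 7.8% at 12 months, and 1 − 0.75^0.75 = 19.4% v 1 − 0.85^0.75 = 11.5% at 24 months. Power at 247 per arm falls from 79.5% to 52.4% and 68.5% respectively.

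**The case against.** A reader might infer that late leavers are scored as retained. They are not. Retention is a separate primary measure, and the visits these women miss lower it. They are only not yet lost on the binary measure.

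A reader might also infer that any SMS effect on leaving in months 6–12 and 18–24 goes unseen. That is too strong: the retention analysis covers both periods, and women who leave in months 6–12 and stay away appear in the 24-month loss row.

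Four further objections carry some weight.

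- The SAP does not forbid confirming a 12-month absence with later records, so this is partly an unspecified rule. But the 0–365 day window is the only instruction given, and two programmers could read it differently.
- Unseen for 6 months as of month 12 is a coherent status definition. It is not what a reader takes from a proportion lost by 12 months.
- The 25 per 100 person-years may already describe loss under the 6-month rule, in which case subtracting a further 6 months counts the lag twice. This weakens the percentages and powers, but not the cut-off days.
- Records may run past day 730: clinic cards are photographed at study exit, and Table 5.2 has a viral-load row at 850 days, although SAP 5.3 says 730. If attendance data do extend that far, part of the 24-month gap could be closed.

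**Conclusion.** The point holds for the binary loss measure. As written, its rows capture departures up to about day 183 and day 548, not day 365 and day 730. Only women who leave in months 18–24 are missed by that measure altogether.

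The cut-off days follow from the definition and the windows alone. The sizes in the table are illustrative: they rest on a constant hazard, no return to care, and reading the SAP's rate as a departure rate. The ranges reflect the unknown antenatal time at risk and whether 247 or 275 women per arm are analysed. The higher number is arguable, because loss is itself the event and comes from records.

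The documents do not support a claim of bias between arms. The lag is the same in each arm, and the risk ratio changes by less than 0.02 in this illustration. Bias would need arms that differ in when women leave, on which the documents give no data. The harm is understated loss, mislabelled rows and lower power. The 12-month part can be recovered; the 24-month part cannot be unless attendance records continue beyond day 730.

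**What to change.** In SAP section 2, SAP 5.3 and Table 5.2:

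- Date loss at the last clinic visit before an absence of at least 6 months, and say whether a later return cancels it.
- For the 12-month row, count women whose last visit before such an absence fell on or before day 365, using attendance records to month 18 (365 + 182 = day 547). These records are already abstracted. This restores the 12-month events; in the illustration, power rises from 31.4% to 53.0% at one end of the range and from 57.5% to 72.8% at the other.
- For the last row, state that it reflects departures up to about month 18 (last visit by about day 548), unless attendance records past day 730 exist to confirm later absences. This corrects the label only. It counts the same women and recovers no power.

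Log the change in SAP section 6. The cost is wording and programming, with no new data collection. The drawback is that the final loss row then describes about 18 months rather than 24; the visit-based retention measure still covers the full period.
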